For the secondary biological study, a sample size of 60 subjects in each group, women with anxiety (with and without intervention) and healthy controls, will give us at least 80% power to detect a difference in means of log-transformed cytokines across groups with an effect size of 0.3 to 0.5. This calculation assumes four repeated measurements with exchangeable covariance structure, a correlation of 0.6 and alpha level = 0.05. The smallest observed effect size for CCL3 between anxious and non-anxious women in the preliminary data of 51 women was 0.3 in 1nd trimester to 0.5 in the 2nd trimester (Cohen's D from 0.3 to 0.5). Sample size calculations were performed using the PASS Sample Size Software program.(34) Prior studies in our clinic have an attrition rate of up to 20%, but because the attrition rate for this type of study in Pakistan is unknown we will increase our sample size to account for higher attrition (up to 40%). We will therefore enroll 300 women to yield an ultimate sample size of at least 180.

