#### Analysis of Variables from Biological Substudy

**Statistical Analysis.** Oversight for the statistical analyses will be provided by [name] of the Johns Hopkins Biostatistics Center. The initial statistical approach will include a descriptive cross-sectional analysis at each time point, both for quality assurance and to attain a better understanding of the distributions of the outcome variables for use in subsequent analyses, including the need for any transformations, followed by the longitudinal analyses. For **Aim 1**, we will assess the associations between cytokine levels as dependent variables and level of anxiety (as measured by the HADS) as the independent variable. The level of anxiety will be considered from the following perspectives: 1) dichotomous (above and below HADS=8) and 2) continuous. In both analyses, we will compare women with anxiety vs. healthy controls and with and without the intervention to evaluate whether there is a positive association between

cytokines and other immune markers with anxiety. In addition, we will perform a comparison of immune markers between women disease/intervention groups adjusted for potential confounders that are differentially distributed by disease group, using multivariable linear regression model at each time point. We will assess whether association between immune marker and anxiety is different by group and by visit. In the longitudinal analyses, we will fit generalized linear mixed effect models to account for within-woman correlation of inflammatory markers. The model will include indicators for visit and group as well as any relevant interaction terms (e.g. group by visit). The models will adjust for baseline severity and other patient characteristics. A random effect for woman will be included as a random intercept. Other, more complex model structures will be explored, such as a model with random slope or non-independent residual correlation structure. These models account for missing at random, i.e. missing data are assumed to depend on prior immune marker values and covariates. Standard model checking will be performed and the most parsimonious model will be selected based on the Akaike Information Criterion (AIC).

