**Biological Outcome Variables:** Subjects will have their blood drawn (up to 20 ml) at all four visits by a study clinician or a research assistant trained in phlebotomy. Each participant will be scheduled as close to possible to the same time of day during the morning hours for all four blood draws (as blood is drawn in HFH between 8:00am and 1:00 pm), allowing us to control for diurnal variation in cytokine levels. Blood will be collected in sodium-heparin tubes for immune cell preparation. Blood will be centrifuged within 8 hours of collection by low-density gradient centrifugation via a Z326 High Performance Centrifuge. Plasma will immediately be frozen in cryovials at -80 C in a ThermoScientific Revco RLE Ultra-Low Lab Freezer and will be stored there until it is shipped to Baltimore for analysis at the end of the trial.

**Shipping of Samples:** Plasma samples (approximately 4800 cryovials) will be shipped from Pakistan to Baltimore at the end of the trial for analysis using Federal Express courier services. Blood will stay frozen at a minimum of -20 throughout shipment, using standard cold packs, dry ice, or liquid nitrogen as required by local regulations and the standards of the courier services. Because we will not be able to maintain a temperature of -80 during shipping, we plan to use multiple shipments (6-8) so that we can initiate analysis immediately upon arrival in Baltimore to avoid freeze-thaw cycles. (Shipping all vials at once will yield a batch too large for the capacity of our laboratory and staff to process at once.) Leftover samples will be refrozen for possible additional future analyses and will be stored in [name] lab at the Women's Mood Disorders Center, Johns Hopkins School of Medicine.

**Blood Sample timing:** Targets times for sampling blood will be at baseline (between 10 and 22 weeks), during the second trimester (24 weeks  $\pm$  2), the third trimester (36 weeks  $\pm$  2) and at 6 weeks  $\pm$  2 postpartum). All samples will be drawn in the morning (between 8:00 am and 1:00 pm) to minimize differences due to diurnal fluctuations in cytokine levels.

- If genetic/genomic analyses are planned, address whether the data will be contributed to a GWAS or other large dataset. Address returning unanticipated incidental genetic findings to study participants.

N/A

- If clinical or laboratory work will be performed at JHU/JHH, provide the JH Biosafety Registration Number.

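### The biological substudy's claim of at least 80% power at 60 per group holds at d = 0.5 but not at a constant d = 0.3, where power is about 50% to 62%

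*Combined protocol and SAP*

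**What the plan says.** The power statement for the secondary biological study is in Section III.B. The design is "a sample size of 60 subjects in each group, women with anxiety (with and without intervention) and healthy controls", and the claim is "at least 80% power to detect a difference in means of log-transformed cytokines across groups with an effect size of 0.3 to 0.5". The technical inputs follow: "This calculation assumes four repeated measurements with exchangeable covariance structure, a correlation of 0.6 and alpha level = 0.05".

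The effect-size range comes from pilot work: "The smallest observed effect size for CCL3 between anxious and non-anxious women in the preliminary data of 51 women" was 0.3 in the first trimester and 0.5 in the second, and the metric is identified as Cohen's d. Attrition of up to 40% is then allowed for: "We will therefore enroll 300 women to yield an ultimate sample size of at least 180".

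Two later parts of Section V bear on this. Under Blood Sample timing, the first of the four draws is the baseline sample ("Targets times for sampling blood will be at baseline (between 10 and 22 weeks" of gestation), followed by draws at about 24 weeks, 36 weeks and 6 weeks postpartum. Under Analysis of Variables from Biological Substudy, the Aim 1 plan is that "we will compare women with anxiety vs. healthy controls and with and without the intervention", using a mixed model with a random intercept for each woman: "The model will include indicators for visit and group as well as any relevant interaction terms (e.g. group by visit".

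**The concern.** A claim of at least 80% power over a range of effect sizes promises 80% at the bottom of the range. Here the bottom is the smallest effect seen in the pilot data, so 0.3 reads as a real target. With four measures correlated at 0.6, repeated sampling removes only 30% of the variance of a single measure, and 60 per group then looks too few for d = 0.3.

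The paragraph also leaves out what is needed to check the figure: the contrast powered, the sidedness, the test, and the difference assumed at each draw. The analysis plan has two contrasts, but the only effect size supplied is for anxious versus non-anxious women.

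If the claim is wrong at 0.3, a true anxious-versus-healthy difference of that size would be missed about four times in ten (pooled) or half the time (one anxious group). A reader relying on the stated 80% could then take a null marker result as stronger evidence of no difference than it is.

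**Working it through.** **Inputs from Section III.B.** 60 per group in three groups (120 anxious if pooled, 60 healthy); four measures; exchangeable correlation 0.6; alpha 0.05; Cohen's d of 0.3 to 0.5. Two-sided testing is assumed because sidedness is not stated.

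**Attrition step.** 300 × (1 − 0.40) = 180, or 60 per group. This reproduces the plan's figure.

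**Variance of a woman's four-draw mean, in single-measure SD units.** v = (1 + 3 × 0.6)/4 = 0.70. With d constant and exchangeable correlation, the four-draw mean is the efficient summary, so no other analysis of these four measures alone does better.

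**Standard errors.**
- Pooled, 120 vs 60: √[0.70 × (1/120 + 1/60)] = 0.1323
- One anxious group, 60 vs 60: √[0.70 × 2/60] = 0.1528

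**Power** = Φ(d/SE − 1.96) + Φ(−d/SE − 1.96), constant d:

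| d | 120 vs 60 | 60 vs 60 |
|---|---|---|
| 0.3 | 62% | 50% |
| 0.4 | 86% | 74% |
| 0.5 | 97% | 91% |

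The claim reproduces at 0.5 and not at 0.3. Noncentral-t power agrees to within one percentage point, and a 20,000-replicate simulation gave 62% and 49% at d = 0.3.

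**Detectable d at 80% power** = (1.96 + 0.842) × SE: 0.371 pooled, 0.428 for 60 vs 60.

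**Other readings at d = 0.3.**
- One-sided alpha 0.05: 73% pooled, 63% for 60 vs 60.
- Three-group F test (2 and 177 df), both anxious groups shifted equally: 51% (93% at d = 0.5).

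**Visit-profile reading.** Power then depends on the mean d over the four draws. The documents give no values for the last two draws, so these are assumptions:

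| d at draws 1 to 4 | mean d | 120 vs 60 | 60 vs 60 |
|---|---|---|---|
| 0.3, 0.5, 0.5, 0.5 | 0.45 | 93% | 84% |
| 0.3, 0.5, 0.4, 0.4 | 0.40 | 86% | 74% |
| 0.5, 0.5, 0.3, 0.3 | 0.40 | 86% | 74% |
| 0.3, 0.5, 0.3, 0.3 | 0.35 | 75% | 63% |

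With 0.3 and 0.5 at the first two draws, the last two must average at least (4 × 0.371 − 0.8)/2 = 0.34 pooled, or (4 × 0.428 − 0.8)/2 = 0.46 for 60 vs 60. With 0.5 at both early draws, they must average about 0.24 or 0.36.

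**Better retention, constant d = 0.3.** At 20% attrition (80 per group): 74% pooled, 62% for one group. With no attrition (100 per group): 83% and 72%.

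**Pooling assumption.** The pooled figures take both anxious groups to differ equally from healthy controls. Suppose the treated group's 0.3 shrinks by a common factor at the three later draws (assumed). If halved, its mean d is (0.3 + 3 × 0.15)/4 = 0.1875, the pooled d is (0.3 + 0.1875)/2 = 0.244, and power is 45%. If abolished, these become 0.075, 0.1875 and 29%. The range is 62% (no attenuation) to 29% (full).

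**The case against.** The strongest reply is that 0.3 to 0.5 was never meant as a constant effect. The text ties 0.3 to the first trimester and 0.5 to the second, and the baseline window of 10 to 22 weeks lies mostly in the second trimester. On that mapping, 0.5 could apply to much of the first draw as well as the second, and a constant 0.3 carries a first-trimester value to draws taken later. This is a fair reading, and under some such profiles the power exceeds 80%. But the paragraph does not say a profile was used and gives nothing for the last two draws, so the 80% cannot be confirmed this way either.

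A second reply is that the model is unknown. A baseline-adjusted comparison with one baseline and four later measures gives 80.5% at d = 0.3 with 60 per group. That needs five measures, and the design has four including baseline. With three later draws the figures are 77% for 60 vs 60 and 87% pooled, but only if the groups do not differ at baseline, which does not fit anxious versus healthy. If d = 0.3 is also present at baseline, the adjusted difference is 0.3 × (1 − 0.6) = 0.12 and power is 19% to 24%.

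Third, 60 is a cautious floor: the investigators' earlier studies lost up to 20%. That is true, and pooled power at d = 0.3 passes 80% with full retention. The stated claim, however, is attached to 60 per group.

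It is also fair to say that this is a mechanistic substudy and that no decision in the plan is made to depend on a null marker result. That limits the consequence and does not make the figure right.

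**Conclusion.** The concern holds. At 60 per group and a constant d = 0.3, time-averaged power for anxious versus healthy is about 62% with the anxious groups pooled and 50% with one anxious group, against a stated minimum of 80%. At d = 0.5 the claim is met. These figures assume two-sided alpha 0.05, exchangeable correlation 0.6, all four draws and, for the pooled figure, equal differences in both anxious groups. The shortfall remains under one-sided testing and under a three-group test.

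The claim can be true under a visit profile whose mean d reaches about 0.37 (pooled) or 0.43 (one group), but no four-visit profile is stated. So the sentence is either wrong at its lower end or rests on inputs that are not given.

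The stated power also cannot be carried to intervention versus enhanced usual care. No effect size is given for that contrast, and the first of its four draws is the baseline sample. The point concerns the secondary substudy only.

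**What to change.** Reword the power paragraph for the biological study in Section III.B so that it names the contrast, the test and the sidedness. Then do one of the following.

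- **If a constant effect was meant,** restate the detectable difference. For example: with 60 women per group, four measures, correlation 0.6 and two-sided alpha 0.05, the time-averaged anxious-versus-healthy comparison has 80% power at d of about 0.37 (anxious groups pooled, assuming both differ equally from healthy controls) or 0.43 (one anxious group); at a constant d = 0.3, power is about 62% and 50%.
- **If a visit profile was meant,** give the assumed d at each of the four draws and the power under it.

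In either case, say that the figure does not apply to intervention versus enhanced usual care. Any power for that contrast should be given separately, with its own effect size and the mixed model planned for Aim 1.

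The cost is one reworded paragraph and, under the constant-effect reading, a less favourable stated power at d = 0.3. Enrolment stays at 300, no new data are needed, and the main trial is unchanged.

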This IRB application also covers a secondary study, to additionally study biological correlates of antenatal anxiety (i.e., immune and endocrine functioning) in a subset of women from the main trial: 200 drawn from our randomized trial (100 intervention, 100 usual care), as well as 100 healthy women without anxiety or depression. The aims of the secondary study are as follows:

**Aim 1:** To characterize the “immune phenotype” of anxious women across the peripartum, specifically by measuring the relation among anxiety symptoms and peripheral markers of inflammation (IL-6, CCL3, CXCL8, Eotaxin, VEGF, and GM-CSF, as supported by our preliminary data) within and across women (both anxious and healthy) and between those receiving the intervention and control.

**Aim 2:** To determine the relation between levels of allopregnanolone (ALLO) in pregnancy and 1) concurrent anxiety symptoms and 2) future symptoms of postpartum depression (PPD).

**Aim 3:** To examine the relation between changes in immune functioning (Aim 1) and ALLO levels (Aim 2) in anxious pregnancy across time.

**Aim 4:** To examine whether immune function and/or ALLO are mediators or moderators of the association between antenatal anxiety and poor birth outcomes (specifically, preterm birth and small-for-gestational age).

To supplement our study, we will collect qualitative data as part of a process evaluation to better understand women's experiences with the intervention (e.g. how it can be improved). Given the recent effects of COVID-19 on our participants and our study, we will also inquire about how the telephone format of our intervention is being received by our participants, as well as try to learn about the impact of social-distancing and other aspects of the COVID-19 situation on pregnant women generally.

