participants (e.g. to improve our intervention regarding this issue) we have also included some questions on this topic in our interview guide. If women have a lot to say and are tired or it is more convenient for them to do the interview in two telephone calls (one regarding questions on implementation of the intervention and the other on COVID-19) we will offer them to option to participate in two shorter interviews rather than one long one.

For the secondary biological study, we will be examining features of immune and endocrine system alteration in women enrolled in this trial to determine 1) whether there is a pattern of immune dysregulation common to women with antenatal anxiety 2) whether our intervention alters that pattern 3) whether immune dysregulation is related to dysregulation of allopregnanolone and 4) whether these biological mechanisms are mediators or moderators of the success of the intervention in reducing poor birth outcomes. We plan to recruit 300 pregnant women in three groups: 100 will from the intervention group, 100 will be from the enhanced usual care (EUC) group, and 100 will be healthy controls (pregnant women who have scored <8 on both anxiety and depression subscales of the HADS). Participants in the biological study will have their blood drawn at all four study visits; blood will be frozen as plasma at -80 and will be shipped to Johns Hopkins for immune and endocrine analyses.

- B. Provide a sample size and a justification as to how you arrived at that number. If you use screening procedures to arrive at a final sample a table may be helpful.

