In our study, the unit of randomization is an individual woman, with an equal number of women randomized to the intervention and control groups. We assume an outcome prevalence of CMDs (postnatal depression episode and anxiety) at 30%, which is conservative given that most estimates of prenatal depression in Pakistan are higher than this. (16, 17, 91, 129) While we observed a 50% reduction in postnatal depressive symptoms when evaluating our prior CBT intervention (which was initiated late in pregnancy), we desire 85% power to detect reductions in CMDs as low as 30% (86, 130, 131), requiring 840 pregnant women (420 in each arm). Anticipating 30% attrition post enrollment, we will enroll 600 women per group in this study, for a total of 1200 women. This sample size of 420 outcomes per group provides ample power to detect important reductions in SGA, which we currently estimate to occur in approximately 47% of births. For example, we will have 90% and 80% power to detect reductions of 23.7% and 20.2%, respectively.

Sample size considerations for the qualitative process evaluation/COVID-questions will be based on a target number of up to 80 women sampled across different characteristics, or until saturation is achieved. We will sample up to 45 women from the intervention group and 25 women from the EUC group and another 10 who dropped out of the intervention. As described (See under Study Design above), these women will be purposively sampled to achieve a wide range of variation (or maximum variation) on various dimensions of interest. To triangulate and learn from multiple perspectives, we will also hold 2 focus group discussions (FGDs) with the HMHB therapists and assessors/screeners involved in delivery, assessments, or coordination of the intervention to ask them about their perspective on the same issues. Topics of interest for sub-group analyses include the effects of transitioning from in-person to by-phone format during the COVID pandemic, distress related to COVID-19, and the effects of prior miscarriage on current pregnancy and intervention experience.

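### The biological substudy's 80% power figure is applied to HMHB versus EUC, but its effect size is an anxious versus non-anxious gap, and 80% is not reached at d = 0.3

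*Combined protocol and SAP*

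**What the plan says.** The substudy paragraph of section III.B makes one power statement. It is based on "a sample size of 60 subjects in each group, women with anxiety (with and without intervention) and healthy controls", and claims "at least 80% power to detect a difference in means of log-transformed cytokines across groups with an effect size of 0.3 to 0.5". The stated assumptions are "four repeated measurements with exchangeable covariance structure, a correlation of 0.6 and alpha level = 0.05"; whether the test is one- or two-sided is not given. The effect size has a single source: "The smallest observed effect size for CCL3 between anxious and non-anxious women in the preliminary data of 51 women was 0.3" in early pregnancy, rising to 0.5 in the second trimester, both given as Cohen's d. Enrolment is 300, so that at least 180 remain after up to 40% attrition.

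The intervention contrast is part of the substudy's purpose. Aim 1 in section I includes marker comparisons "between those receiving the intervention and control", and section III.A lists as a question "whether our intervention alters that pattern". The substudy analysis text in section V plans comparisons with and without the intervention. It uses mixed models with group, visit and their interaction, adjusted for baseline severity. The blood-sampling schedule in section V places the first of the four draws at baseline.

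**The concern.** The power statement names the two anxious arms separately, so a reader will take the 80% to apply to HMHB versus EUC. Its effect size, however, describes how anxious women differ from non-anxious women, which is an observational contrast. Both randomised arms are anxious at entry (HADS anxiety of 8 or more). No section states how far HMHB is expected to shift any marker, and none gives power for the shift.

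HMHB versus EUC is the only randomised comparison in the substudy and the one that speaks most directly to whether the intervention changes biology. If 80% is taken at face value, a non-significant result there could be given more weight than the design supports.

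**Working it through.** **Inputs.** From section III.B: 60 per group, four draws, exchangeable correlation 0.6, alpha 0.05, d from 0.3 to 0.5. Two-sided testing is my assumption. The enrolment figure reproduces: 180/(1 − 0.40) = 300.

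**Formula.** Power = Φ(d/SE − 1.96), where SE = √(V × (1/n₁ + 1/n₂)) and V is the variance of the summary measure in units of the single-draw variance. The smallest d detectable with 80% power is 2.80 × SE.

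**Step 1: the plan's own 80%, as a mean over four draws.** V = (1 + 3 × 0.6)/4 = 0.70.
- 60 versus 60: SE = √(0.70 × 2/60) = 0.153. Power is 50% at d = 0.3 and 91% at d = 0.5; detectable d is 0.43.
- 120 anxious versus 60 healthy: SE = √(0.70 × (1/120 + 1/60)) = 0.132. Power is 62% at d = 0.3 and 97% at d = 0.5; detectable d is 0.37.
- Three-group F test with both anxious arms at the same mean: 51% at d = 0.3 and 93% at d = 0.5.

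The stated 80% holds at d = 0.5 but does not reproduce at d = 0.3, which would need 123 per group. One-sided testing at d = 0.3 gives 63% (60 versus 60) or 73% (120 versus 60). At d = 0.3, 80% was reached only by reading 0.3 as Cohen's f (99%), by treating the four draws as independent (91%), or by ignoring attrition (100 versus 200, 83%; one-sided 100 versus 100, 81%). Each conflicts with a stated input: Cohen's d, correlation 0.6, or 60 per group.

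**Step 2: HMHB versus EUC.** The baseline draw cannot carry an intervention effect, so the three later draws are used.
- Unadjusted: V = (1 + 2 × 0.6)/3 = 0.733, SE = √(0.733 × 2/60) = 0.156.
- Adjusted for the baseline marker: V = 0.733 − 0.6² = 0.373, SE = √(0.373 × 2/60) = 0.112.

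| | d = 0.3 | d = 0.5 | Detectable d, 80% power |
|---|---|---|---|
| Three draws, unadjusted | 48% | 89% | 0.44 |
| Three draws, baseline marker adjusted | 77% | 99% | 0.31 |

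**Step 3: a conditional illustration.** Suppose HMHB closed only part of the anxious–healthy gap. The share closed is an assumption; the documents give none for any marker.

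| Share closed × gap | d | Unadjusted | Adjusted |
|---|---|---|---|
| 30% × 0.3 | 0.09 | 8% | 12% |
| 30% × 0.5, or 50% × 0.3 | 0.15 | 16% | 27% |
| 50% × 0.5 | 0.25 | 36% | 61% |

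**The case against.** The strongest reply is that no low power figure for HMHB versus EUC is a fact of the documents. A reader might infer that power for the intervention question is simply somewhere below 40%. That needs an assumed 30–50% closure of the gap and an unadjusted analysis. The 30% and 50% in the main sample-size paragraph are reductions in CMDs and in depressive symptoms; neither converts to a share of a standardised log-cytokine difference. This stands, so Step 3 is an illustration only.

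A reader might also infer that d = 0.3 to 0.5 is attainable only if HMHB removes the whole anxious–healthy gap. The documents do not support that either. The gap is given for CCL3 alone, one of six markers in Aim 1, and is called the smallest observed. It is a ceiling only if HMHB works by moving anxious women toward control levels. Session 2 in Table 1 also targets diet, rest and sleep, and section II says sleep and nutrition may be related to inflammation.

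Three further points are fair. Sixty per group is a floor: with no attrition (100 per arm) and baseline adjustment, power at d = 0.3 would be about 93%. Adjustment for baseline severity may be meant to include the baseline marker, in which case the shortfall at d = 0.3 with 60 per arm is about 3 points (77% against 80%). And no section says that a null marker result will be read as absence of effect.

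What remains is that the one power statement covers a contrast for which the plan supplies no effect size. The figure also misses 80% at the low end of its own range for every contrast checked at 60 per group.

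**Conclusion.** The concern holds in a limited form, as two distinct problems. First, the substudy's 80% extends to HMHB versus EUC although its effect size belongs to anxious versus non-anxious women, and the plan states no HMHB effect on any marker. This is plain from the text and needs no calculation. Second, with 60 per group, correlation 0.6 and two-sided alpha 0.05, the 80% is not delivered at d = 0.3. Power there is 48% for HMHB versus EUC unadjusted and 77% with baseline-marker adjustment; for anxious versus healthy it is 50–62%. At d = 0.5 power is adequate throughout.

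If HMHB closed 30–50% of a 0.3–0.5 gap, power would be about 8–36% unadjusted or 12–61% adjusted. That range is conditional on the assumed closure and should not be quoted as the substudy's power.

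**What to change.** In the substudy paragraph of section III.B:

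1. Tie the 0.3–0.5 effect size to the anxious versus healthy comparison and correct the power: about 50% at d = 0.3 for 60 versus 60 and 62% for 120 versus 60, with 80% reached only from about d = 0.43 or 0.37 respectively.
2. Add a separate line for HMHB versus EUC: with 60 per arm, the smallest d detectable with 80% power is about 0.44, or 0.31 if the model adjusts for the baseline marker. Say in the Aim 1 analysis text which of these applies.
3. Label that contrast exploratory, report it as an estimate with a confidence interval, and state that a non-significant result will not be read as no biological effect. The plan already calls its mediation and moderator analyses exploratory because of limited power.

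This is a change of wording, with no extra women, visits or assays. The cost is a less favourable stated power.
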